#### Handling of missing data:

Missing information will be captured for quantitative as well as qualitative variables by the category "Missing" in the summary statistics. If there are no missing values this will be indicated by "0". Missing data will not be imputed. Missing statistics, e.g. when they cannot be calculated,

should be presented as "nd". For example, if n=1, the measure of variability (SD) cannot be computed and should be presented as "nd".

All analyses will be performed using SAS® Software version 9.1.3 or higher.

#### 10 Trial Subjects

#### 10.1 Disposition of Subjects and Discontinuations

A table with

- Number of subjects screened
- Number of subjects with screen failure
- Number of subjects enrolled in the study
- Number of subjects randomized in the study
- Number of subjects in Full Analysis (FA) dataset
- Number of subjects in Per Protocol (PP) dataset
- Number of subjects completed the study as per protocol
- Subject completed the study as per protocol and appropriate outcome (Failed to conceive/ Biochemical pregnancy/ Spontaneous Miscarriage/ Clinical pregnancy/ Ongoing pregnancy/ Subject underwent therapeutic abortion/elective abortion)
- Number of subjects who discontinued from the study
- Subject did not complete the study as per protocol and appropriate outcome (Fresh embryo transfer was cancelled/ Subject requested to be withdrawn after embryo transfer/ Investigator withdrew subject/ Imaging was discontinued prior to completion/ Subject was lost to follow-up/ Subject was non-compliant/ Other)
- Fresh embryo transfer was cancelled, appropriate reason (No cleavage/ No viable embryo for transfer/ Freeze all due to elevated risk of OHSS/ Other)

will be summarized as number and percentage for both the treatment groups and overall.

Subjects Screened are the subjects for whom "Date informed consent signed by subject/partner" is available.

Subjects enrolled in the study are the subjects who satisfy both the inclusion and exclusion criteria.

Screen failure subjects are the subjects who are screened but not satisfying any one of the inclusion or exclusion or both criteria.

Listing will be provided for details of randomized subjects from (FA) dataset.

#### 10.2 Protocol Deviations

#### 10.2.1 Major Protocol Deviations

The following summary table and listing of major protocol deviations will be provided for both treatment groups and overall:

- Frequency table per reason of major protocol deviations
- Listing of major protocol deviations

# 10.2.2 Reasons Leading to the Exclusion from an Analysis Set

For subjects excluded from the PP, the reasons for exclusion will be summarized by treatment groups and overall and a listing also will be provided for the same.

- Frequency table per reason of exclusion from the PP population
- Listing of reasons of exclusion from the PP population

# 11 Demographics and Other Baseline Characteristics

# 11.1 Demographics

The quantitative variables

- Age (years)
- Body weight (kg)
- Height (cm)

• BMI  $(kg/m^2)$ 

will be summarized by using descriptive statistics for both treatment groups and overall from (FA) dataset.

Age (years) = (Date informed consent signed by Subject (Female) or Partner- Date of Birth (Subject) + 1/ 365.25.

If day is missing for either date of informed consent or date of birth, then it will be replaced by 1st day of the month. Similarly, missing month will be replaced by 1st July of the year.

The qualitative variable

• Current smoker (Yes/No)

will be summarized by using number and percentage for both treatment groups and overall from (FA) dataset.

### 11.2 Medical History

#### **Cause of Infertility:**

The quantitative variable

• Duration of infertility (Months)

will be summarized by using descriptive statistics for both treatment groups and overall from (FA) dataset.

The qualitative variables

- Type of infertility (Primary infertility/ Secondary infertility)
- Reasons of infertility (Male factor/ Tubal factor/ Endometriosis/ Anovulation/ Unexplained/ Other)

will be summarized by using number and percentage for both treatment groups and overall from (FA) dataset.

Listing will be provided for Cause of Infertility from (FA) dataset.

#### **Obstetrical History:**

The quantitative variables

- Number of previous pregnancies
- Number of live births
- Number of spontaneous miscarriages
- Number of therapeutic/elective abortions
- Number of stillbirths
- Number of ectopic pregnancies
- Number of multiple pregnancies
- Number of babies with congenital anomalies
- Prior Gonadotropin cycles (non-ART)
- Prior fresh ART cycles
- Prior frozen ART cycles

will be summarized by using descriptive statistics for both treatment groups and overall from (FA) dataset.

The qualitative variable

• Subject has obstetrical history (Yes/ No)

will be summarized by using number and percentage for both treatment groups and overall from (FA) dataset.

Listing will be provided for Obstetrical History from (FA) dataset.

#### 11.3 Other Baseline Characteristics

#### **Cycle Day 2-4 hormones:**

Listing will be provided for Cycle Day 2-4 hormones from (FA) dataset.

#### **Antral Follicle Count:**

The quantitative variable

• Total AFC (Only follicles between > or = 2mm and < 11mm)

will be summarized by descriptive statistics for both treatment groups and overall from (FA) dataset.

The qualitative variable

• Day of menstrual cycle for Assay (1/2/X/X)

will be summarized by using number and percentage for both treatment groups and overall from (FA) dataset.

#### 12 Previous or Concomitant Medications/Procedures

Not Applicable.

# 13 Treatment Compliance and Exposure

Treatment is defined as the process of embryo culture and assessment, whereas no trial medication is applied in this trial.

#### **COS** and Ovulation triggering Visit:

#### **Down Regulation:**

The qualitative variable

• Type of Protocol (Antagonist protocol/ Long agonist protocol/ Other)

will be summarized by using number and percentage for both treatment groups and overall from (FA) dataset.

Listing will be provided for Down Regulation, Controlled Ovarian Stimulation and Ovulation triggering from (FA) dataset.

#### Ovulation triggering and luteal phase support (LPS):

The qualitative variables

- Luteal phase support (Ovulation triggering with hCG/ Ovulation triggering with GnRH-a/ No LPS)
- LPS after Ovulation triggering with hCG
  - o Vaginal micronized progesterone gel
  - Vaginal progesterone capsule/tablet/suppository
  - o Intramuscular progesterone
  - o Other
- LPS after Ovulation triggering with GnRH-a (hCG/ Vaginal micronized progesterone gel/ Estradiol/ Other)

will be summarized by using number and percentage for both treatment groups and overall from (FA) dataset.

Listing will be provided for Luteal phase support (LPS) from (FA) dataset.

#### **Eeva conformity:**

The qualitative variables

- Eeva conformed subjects
- Eeva non-conformed subjects

will be summarized by using number and percentage for GERI+ Incubator treatment group from (FA) dataset.

Eeva conformed subjects: embryo transfer is based on Eeva result applied to good and fair quality embryos.

Eeva non-conformed subjects: embryo transfer is not based on Eeva result (when either of the boxes in the last two columns of eCRF CP6 is ticked).

#### 14 Efficacy Analyses

# 14.1 Clinical Pregnancy with positive fetal heartbeat (Primary Endpoint)

The primary end point is clinical pregnancy with positive fetal heartbeat. It is defined as the pregnancy diagnosed by ultrasonographic or clinical documentation of at least one fetus with heart beat in gestational week 6 to 8. It includes ectopic pregnancy.

The qualitative variables

- Ultrasound performed (Yes/No)
- Result of ultrasound (Biochemical pregnancy/ Ectopic pregnancy/ Intrauterine clinical pregnancy (with and without positive FHB)/ Clinical pregnancy (FHB positive or negative intrauterine pregnancy + ectopic pregnancy)/ Other)
- Number of subjects with Embryo transfer attempted (Yes/No)
- Subjects with FHB positive clinical pregnancy

will be summarized by using number and percentage for both treatment groups and overall from (FA) dataset and (PP) dataset.

The quantitative variables

- Number of intrauterine gestational sacs
- Number of sacs with fetal heartbeats

will be summarized by using descriptive statistics for both treatment groups and overall from (FA) dataset and (PP) dataset.

The quantitative variable

• FHB positive Clinical pregnancy rate (%)

will be summarized by percentage for both treatment groups and overall from (FA) dataset and (PP) dataset.

No. of subjects with clinical pregnancy = Intrauterine clinical pregnancy subjects (with and without positive FHB) + Ectopic pregnancy subjects.

**Subject with FHB positive clinical pregnancy** = Intrauterine Clinical Pregnancy subject with at least one or more sacs with fetal heartbeats

FHB positive clinical pregnancy rate (%) = No. of subjects with FHB positive clinical pregnancy)/ No. of subjects with embryo transfer)\* 100.

No. of subjects with embryo transfer = Subjects with embryo transfer attempted.

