8.4.2 Analysis of Primary Endpoint

The FHB positive clinical pregnancy rate (the number of subjects with FHB positive clinical pregnancy divided by the number of subjects with embryo transfer) for either of the two treatment groups will be computed.

Primary hypothesis will be tested between the treatment groups based on a Cochrane-Mantel-Haenzel CMH test adjusting for stratification factors providing the derived Odds Ratio and its 95% confidence interval. As sensitivity analysis, a logistic regression model with confounding factors and stratification factors as covariates will be performed. Details regarding the model and analysis will be specified in the SAP.

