8.4.3 Analysis of Secondary Endpoints

- Utilization Rate: the number of transferred and cryopreserved embryos divided by the number of 2PN zygotes per subject.
- Good Quality Embryo Rate: the number of good quality embryos divided by the number of 2PN zygotes per subject.

Protocol Version: 3.0 / Jan 31, 2018 33 / 49

trial

• Non-viable Embryo Rate: the number of non-viable embryos divided by the number of 2PN zygotes per subject.

- FHB positive implantation rate is calculated per embryo transferred (IR) and per subject randomized (IR*):
 - a. IR: the number of gestational sacs with positive FHB under ultrasound scan at gestational weeks 6-8 divided by the total number of embryos transferred.
 - b. IR*: IR_w is calculated for each subject and not aggregated per group of patients. In the scenario where maximally two or maximally three embryos are transferred at once, the IR_w can only have two (0 and 1.0), three (0, 0.5 and 1.0) and four (0, 0.33, 0.66 and 1.0) states, respectively. As such, IR_w is an ordinally scaled categorical event. Then the overall IR* for each treatment group= $(1/n)^* \Sigma_{w=1,n}$ IR_w.
- Biochemical Pregnancy Rate: the number of subjects with biochemical pregnancy divided by the number of subjects with embryo transfer.
- Ongoing Pregnancy Rate: the number of subjects with ongoing pregnancy divided by the number of subjects with embryo transfer.
- Multiple Pregnancy Rate: the number of subjects with multiple pregnancy divided by the number of subjects with ongoing pregnancy.
- Ectopic Pregnancy Rate: the number of subjects with ectopic pregnancy divided by the number of subjects with embryo transfer.
- Spontaneous Miscarriage Rate: the number of subjects with spontaneous miscarriage divided by the number of subjects with clinical pregnancy.

Descriptive statistics for all of the secondary endpoints will be provided. Detailed statistical analysis methods will be specified in the SAP.

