# 7 Changes to the Planned Analyses in the Clinical Trial Protocol

The statistical methods as described in the protocol were adopted and no changes to the planned analyses. However Statistical comparison between groups and confidence intervals will not be performed. No regression models will be constructed in this study.

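### The primary endpoint is stated to include ectopic pregnancy, but the SAP 14.1 derivation counts only intrauterine pregnancies with a heartbeat, and SAP 7 does not list the departure

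*SAP*

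**What the plan says.** Protocol 5.2.1 defines the primary endpoint as a pregnancy with at least one fetus with a heartbeat in gestational weeks 6 to 8, shown by ultrasound or clinical documentation, and states that ectopic pregnancy is included. SAP 14.1 opens with the same definition and the same sentence: "It includes ectopic pregnancy".

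Protocol 8.4.2 gives the rate as "the number of subjects with FHB positive clinical pregnancy divided by the number of subjects with embryo transfer". It does not mention where the pregnancy is located.

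Further down, SAP 14.1 derives the counted event as an "Intrauterine Clinical Pregnancy subject with at least one or more sacs with fetal heartbeats". This is the numerator of the heartbeat-positive rate. Ectopics enter only a separate total, the number of subjects with clinical pregnancy: "Intrauterine clinical pregnancy subjects (with and without positive FHB) + Ectopic pregnancy subjects".

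SAP 7 states: "The statistical methods as described in the protocol were adopted and no changes to the planned analyses". The exceptions it then names are group comparisons, confidence intervals and regression models. The endpoint definition is not among them.

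**The concern.** The rule that computes the primary rate is not the rule that defines the endpoint, and the two stand in the same SAP section. Neither document says which prevails. A programmer will follow the derivation, while a reader of the report will rely on the definition, and they will disagree about any ectopic pregnancy with a heartbeat.

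SAP 7 also says "However Statistical comparison between groups and confidence intervals will not be performed", so the descriptive rate is the whole primary result. Its numerator should have one documented meaning, chosen before anyone sees results by arm.

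**Working it through.** **The passages side by side, for a woman with an ectopic pregnancy and a heartbeat at weeks 6-8**

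| Source | Counted as a success? |
|---|---|
| Protocol 5.2.1 | Yes: heartbeat present, ectopic included |
| SAP 14.1, opening definition | Yes, same wording |
| Protocol 8.4.2, rate | Not excluded |
| SAP 14.1, derivation | No: must be intrauterine |
| SAP 7, list of changes | Silent |

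**The plan's own figure.** Protocol 8.1 gives 30% in control, a 25% relative increase (0.30 × 1.25 = 37.5%), two-sided alpha 0.05, 80% power and 623 per group. With pooled variance and no continuity correction:

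n = [1.960 × √(2 × 0.3375 × 0.6625) + 0.842 × √(0.30 × 0.70 + 0.375 × 0.625)]² / 0.075² = 622.8, so 623.

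Then 623 / 0.9 = 692.2, so 693 per group and 1,386 in total. The sample size reproduces exactly and is not in question.

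**Size of the conflict: inputs**
- From protocol 8.1: 30%, 37.5% and 623 per arm. The 623 are taken here as women with embryo transfer.
- Assumed, with no source in the documents: ectopic share of clinical pregnancies e = 2-3%; share of ectopics with a heartbeat h = 10-40%; heartbeat-negative intrauterine share f = 5-15% (needed only for reading B).

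Protocol 8.1 speaks only of a clinical pregnancy rate, so both readings were run:
- Reading A: 30%/37.5% are all clinical pregnancies, so C = 623 × p.
- Reading B: 30%/37.5% are heartbeat-positive intrauterine pregnancies, so C = 623 × p / (1 − f − e).

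Here 623 × 0.30 = 186.9 and 623 × 0.375 = 233.6. Women who change status = C × e × h; shift in the rate = that number / 623.

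| | A, control | A, experimental | B, control | B, experimental |
|---|---|---|---|---|
| Clinical pregnancies C | 186.9 | 233.6 | 201.0-227.9 | 251.2-284.9 |
| Ectopics, C × e | 3.7-5.6 | 4.7-7.0 | 4.0-6.8 | 5.0-8.5 |
| Women who change status | 0.37-2.24 | 0.47-2.80 | 0.40-2.74 | 0.50-3.42 |
| Shift in rate (points) | 0.06-0.36 | 0.08-0.45 | 0.06-0.44 | 0.08-0.55 |

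With equal shares in both arms, the planned 7.5-point difference moves by 7.5 × e × h = 0.015 to 0.09 points under A, and by 0.016 to 0.110 points under B. If the shares differed between arms within these ranges, the movement still could not exceed 0.55 points, the largest shift in a single arm.

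**Can the stated endpoint be derived?** Protocol 7.5 lists a number of fetal heartbeats without location and a yes/no item for ectopic pregnancy. SAP 14.1 splits only intrauterine pregnancies by heartbeat: "Ectopic pregnancy/ Intrauterine clinical pregnancy (with and without positive FHB"). The documents do not show whether the heartbeat count is completed for ectopics. The CRF cited in SAP 17 would show it.

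**The case against.** The strongest reply is that this is a wording slip. Only one rule is written as a formula, so the count itself is not in doubt. The intrauterine limit also fits the rest of the SAP: 14.2.4 restricts implantation to intrauterine sacs, and 14.2.8 gives ectopics their own rate. Ectopics appear in the same 14.1 table, so a reader can bound the effect. The number of women is tiny and no test is planned.

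Most of that stands, and it is why the point is small. It does not remove the contradiction. The SAP repeats the inclusive sentence itself, and SAP 7 exists to record such choices.

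Three stronger readings are tempting and are not supported:
- *Every ectopic counts as a success.* Both definitions require a fetus with a heartbeat, so only heartbeat-positive ectopics are at issue.
- *The trial loses power.* The sample size reproduces, the shift is a fraction of a point, and SAP 7 drops the comparison.
- *The miscarriage rate has mismatched parts.* Protocol 8.4.3 and SAP 14.2.9 use "the number of subjects with spontaneous miscarriage divided by the number of subjects with clinical pregnancy". The SAP 14.1 denominator includes heartbeat-negative intrauterine and ectopic pregnancies, and protocol 7.5 exits women with no heartbeat at weeks 6-8, before the weeks 10-12 miscarriage item in 7.6. A reader might infer that their losses can never be counted. But protocol 5.2.2 defines miscarriage as loss of a clinical pregnancy, 6.10 gives it its own exit, 7.5 requires the Trial Exit form, and SAP 10.1 lists spontaneous miscarriage among the completion outcomes. A recording route exists. How it is coded depends on a CRF that is not among the documents, so this is a request for clarification only.

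**Conclusion.** The point holds on the text alone: the SAP 14.1 derivation does not compute the endpoint that protocol 5.2.1 and SAP 14.1 define, and SAP 7 does not declare the change. It should be corrected, because this is the primary numerator and the correction is cheap.

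Its expected size is about 0.4 to 3.4 women per arm, at most about 0.55 points on the rate, and about 0.1 points on the planned difference with equal shares in both arms. These figures rest on the assumed values of e, h and f and hold under either reading of 30%/37.5%. The documents do not show which rule was intended.

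**What to change.** Before database lock and without sight of results by arm, use one rule for the primary numerator:

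1. *Match the definition.* Change the SAP 14.1 derivation to count any pregnancy with a fetal heartbeat at weeks 6-8, including ectopic, as in protocol 5.2.1. First check that the eCRF heartbeat count covers ectopics.
2. *Or keep the intrauterine rule.* Delete "It includes ectopic pregnancy" from SAP 14.1 and, by dated written amendment (protocol 10.6), the same sentence from protocol 5.2.1. Ectopics are then reported only under SAP 14.2.8.

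Either way, enter the decision in SAP 7 and report the rate under the other rule as one sensitivity line.

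Minor clarification: SAP 14.2.9 should confirm that spontaneous losses recorded on the Trial Exit form at the week 6-8 exit count in the miscarriage numerator.

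Cost: one SAP revision and a table line. Option 1 needs no protocol amendment. If the heartbeat count does not cover ectopics, option 1 and the sensitivity line need a query for those cases only, about 4 to 9 per arm under the assumptions above. Option 2 needs a late amendment: SAP 2.0 is dated 14 January 2020, after the planned last-patient-in date of December 2019, and clinicians are not blinded (protocol 6.6), so its timing must be stated. Neither option costs power.

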# 14.2 Day 3 Embryo assessment and Clinical outcome (Secondary Endpoints)

#### 14.2.1 Utilization Rate

Individual Utilization Rate per woman (%) = (No. of Utilizable Embryos per that woman (vitrified and transferred)/ No. of 2PN zygotes per that woman)\*100

will be summarized by using descriptive statistics for both treatment groups and overall from (FA) dataset and PP dataset.

Utilization rate (%) is calculated as the sum of individual utilization rates divided by the number of women

will be summarized for both treatment groups and overall from (FA) dataset and PP dataset.

# 14.2.2 Good Quality Embryo Rate

Individual Good Quality Embryo Rate per woman (%) = (No. of good quality embryos per that woman / No. of 2PN zygotes per that woman)\*100

will be summarized by using descriptive statistics for both treatment groups and overall from (FA) dataset and PP dataset.

Good Quality Embryo Rate (%) is calculated as the sum of individual good quality embryo rates divided by the number of women

will be summarized for both treatment groups and overall from (FA) dataset and PP dataset.

# 14.2.3 Non-viable Embryo Rate

Individual Non-viable Embryo Rate per woman (%) = (No. of non-viable embryos per that woman / No. of 2PN zygotes per that woman)\*100

will be summarized by using descriptive statistics for both treatment groups and overall from (FA) dataset and PP dataset.

Non-viable Embryo Rate (%) is calculated as the sum of individual non-viable embryo rates divided by the number of women

will be summarized for both treatment groups and overall from (FA) dataset and PP dataset.

# 14.2.4 FHB positive implantation rate

FHB positive implantation rate is calculated per embryo transferred (IR) and per subject randomized (IR\*):

- a) IR: the number of intrauterine gestational sacs with positive FHB under ultrasound scans at gestational weeks 6-8 divided by the total number of embryos transferred.
- b) IR\*: Sum of ((Number of intrauterine Gestational Sacs with positive FHB under ultrasound scans at gestational weeks 6-8 at women level/ Number of embryos transferred at women level)\*100) / Number of women who had embryo(s) transfer.

will be summarized for both treatment groups and overall from (FA) dataset and PP dataset.

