6.7 Randomization and Allocation of Subjects

After signing the informed consent form, all eligible subjects will be randomized and allocated to either of the two treatment groups immediately after fertilization check on Day 1 of embryo culture.

A stratified block randomization with fixed block length and allocation ratio 1:1 will be used. The stratification will be based on site and the age of subject (age group 18-35 vs. 36-40). Randomization will be accomplished using the Interactive Web Response Services (IWRS) system. An independent statistician will generate the

Protocol Version: 3.0 / Jan 31, 2018 21 / 49

Study Number: MS200497_0006

randomization schedule and upload to the IWRS system. All randomization codes will not be reused and subjects who discontinue the study early will not be replaced.

A subject can be considered as a drop-out during the study if she is randomized but primary endpoint data is not available for this subject, for whatever reason. Reasons for study discontinuation will be recorded in the Trial Exit eCRF.

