#### 8.2 Definition of Analysis Sets and Subgroups

#### **Full Analysis (FA) dataset:**

(FA) dataset includes all randomized subjects. Subjects will be presented as randomized.

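### IR* carries a per-randomised label, but the SAP formula divides by women with a transfer, so the full-analysis figure is a per-transfer rate

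*SAP*

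**What the plan says.** Protocol 8.4.3 states: "FHB positive implantation rate is calculated per embryo transferred (IR) and per subject randomized". The first version, IR, pools sacs over embryos. The second, IR*, rests on a woman-level value IR_w that "is calculated for each subject and not aggregated per group of patients"; the group figure is (1/n) times the sum of IR_w. The protocol does not define n beyond the label. It lists the possible values of IR_w by the maximum number of embryos transferred and assigns none to a woman who had no embryo transferred.

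SAP 14.2.4 repeats the label ("calculated per embryo transferred (IR) and per subject randomized"). In item (b) it divides the sum of the woman-level rates by the "Number of women who had embryo(s) transfer". The result "will be summarized for both treatment groups and overall from (FA) dataset and PP dataset". In SAP 8.2 the FA "dataset includes all randomized subjects. Subjects will be presented as randomized".

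SAP section 7 says there are "no changes to the planned analyses". It then drops group comparisons, confidence intervals and regression models, and does not mention the IR* denominator.

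**The concern.** The label and the formula describe different populations. Women are randomised "immediately after fertilization check on Day 1 of embryo culture", two days before the planned transfer. SAP 10.1 provides for randomised women whose fresh transfer is cancelled. The reasons it lists include embryos that did not cleave, no embryo fit for transfer, and freezing everything because of hyperstimulation risk. The first two can be results of the culture being compared. Restricting the denominator to women with a transfer is thus a selection after randomisation that the assigned system can influence.

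Among the pregnancy outcomes, IR* is the one that the plan declares per randomised woman. The clinical, biochemical, ongoing and ectopic rates are per woman with transfer; the multiple-pregnancy and miscarriage rates are conditional on pregnancy. As programmed, IR* joins the per-transfer rates. Because SAP section 7 removes tests and intervals, the displayed percentages are the whole result, and a reader will take the label at its word.

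**Working it through.** **Plan's own figures.** The documents give no numerical value for IR*, so there is none to reproduce. The only related calculation is the sample size in Protocol 8.1: 30% versus 37.5% (a 25% relative increase), two-sided alpha 0.05 and power 80% give 623 per group (pooled variance, no continuity correction). Then 623/0.90 = 692.2, rounded up to 693 per group and 1,386 in total. This reproduces exactly and does not involve IR*.

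**Inputs.**
- Declared unit: randomised woman (Protocol 8.4.3; SAP 14.2.4 lead-in).
- Denominator used: women with a transfer (SAP 14.2.4(b)).
- FA set: all randomised women (SAP 8.2).
- t, the share of randomised women with a transfer: not given, so assumed below.

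**Formula.** Let S be the sum of IR_w in an arm, N the women randomised and T = tN the women with a transfer. A woman without a transfer has no implantation from the fresh cycle and adds 0 to S.
- Declared quantity: S/N.
- SAP quantity: S/T = (S/N)/t.
- Ratio of SAP to declared: 1/t.

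**Size of the factor (t assumed).**

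| t | 1/t | Declared value if the SAP formula shows 30% |
|---|---|---|
| 1.00 | 1.00 | 30.0% |
| 0.98 | 1.02 | 29.4% |
| 0.95 | 1.05 | 28.5% |
| 0.90 | 1.11 | 27.0% |

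**Unequal t between arms (all values assumed).**
- Creating a difference: 25% per randomised woman in both arms, no transfer in 5% of one arm and 15% of the other. The SAP formula shows 0.25/0.95 = 26.3% and 0.25/0.85 = 29.4%. The arm that lost more women looks better by 3.1 points. Exchanging the shares reverses the sign.
- Masking a difference: 30% per transfer in both arms with the same shares. The declared quantity is 0.30 × 0.95 = 28.5% against 0.30 × 0.85 = 25.5%, a gap of 3.0 points that the table would show as zero.

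**PP set.** SAP 8.2 requires a transfer for PP membership in both arms, so N and T coincide there and the factor is 1.

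**The case against.** **The protocol left a gap.** It never defines n, and IR_w for a woman with no embryo transferred is 0/0. Its text presents IR* as a woman-level alternative to an embryo-level rate, and the SAP formula delivers that. This stands. A reader might infer that the SAP silently replaced a protocol denominator; the documents do not support that, because the protocol specified the label but not the denominator. What remains is that the SAP filled the gap against the label it repeats. The rule against imputing missing data does not settle the matter either: a woman known to have had no transfer has a known outcome, and scoring it zero defines the endpoint.

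**Nothing is lost from the report.** A reader might infer that the SAP conceals cancelled transfers. It does not. SAP 10.1 tabulates them with reasons by arm, and SAP 14.1 and 14.3.6 tabulate transfer attempted. Multiplying IR* by women transferred over women randomised recovers the declared figure. This also stands; the fault lies in the IR* row.

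**Other rates avoid conditioning on transfer.** The utilisation, good-quality and non-viable embryo rates (SAP 14.2.1 to 14.2.3) are averaged over women from the FA set with 2PN zygotes as the base. So it would be too strong to say that IR* is the only rate able to register a failure of culture.

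**The size is hypothetical.** The 10% in Protocol 8.1 is an allowance for unavailable primary-endpoint data for any reason, and should not be read as a no-transfer rate. Entry requires at least four 2PN zygotes and excludes planned freeze-all cycles, which should keep no-transfer down.

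**The larger choice is elsewhere.** The protocol itself uses women with a transfer for the primary endpoint and several secondary rates. Correcting IR* leaves that untouched.

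**Conclusion.** The inconsistency is real, and no other section resolves it. SAP section 9 makes the analysis set the default denominator unless stated otherwise, and formula (b) states otherwise while keeping the randomised label. Followed as written, the FA row for IR* is a per-transfer rate, too high for its label by 1/t.

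How much too high cannot be derived from the documents. It is nothing if every randomised woman has a transfer, about 5% relative at an assumed t of 0.95, and about 11% at 0.90. A spurious or masked difference between arms needs unequal transfer shares, which are possible but not documented.

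A reader might infer that a randomised test is compromised. That goes too far: IR* is a secondary endpoint, the SAP plans no comparisons or confidence intervals, the sample size does not depend on it, and PP is unaffected. The point is a worthwhile correction to one descriptive statistic and does not threaten the trial's main result.

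**What to change.** In SAP 14.2.4(b), set IR_w to 0 for every randomised woman with no embryo transferred, and divide the sum by all FA women in the arm. This delivers the quantity that the protocol's label declares and closes the gap in its formula.

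If the per-transfer version is also kept, name it *per woman with transfer*, record it in SAP section 7, and print the number of women without a transfer by arm beside it. Relabelling alone would also remove the contradiction, but the plan would then have no pregnancy outcome on the randomised population.

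The cost is one line of the SAP and one denominator in the program. No new data are needed, since transfer status is already collected. The reported rate becomes somewhat lower, by the factor t.
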